4.2. Medical History

Medical history (including general medical history, allergic disease history and history related to aero-allergens) will be coded using Medical Dictionary for Regulatory Activities (MedDRA®).

Information on conditions related to cat allergy will be summarized in medical history, including asthma, allergic conjunctivitis, allergic rhinitis, etc.

4.3. Pre-Treatment / Concomitant Medication/Procedure

Medications/Procedures will be recorded from the day of informed consent until the end-of-study (EOS) visit. Medications will be coded using WHO Drug Dictionary (WHODD). Procedure will be performed based on medical history, adverse event, prophylaxis, and others. Subjects will be counted once in each medication class linked to the medication.

Prior medications/procedures: medications taken, or procedures performed prior to administration of the first dose of study drug.

Concomitant medications/procedures (CMs/CPs): medications taken or procedures performed following the dose of study drug through the EOS visit.

- Concomitant medications/procedures during the 60-week treatment period are medications/procedures taken after the first dose up to the week 60 visit date or date of study day 421 if the week 60 visit date is missing. Medications/procedures taken during the 60-week treatment period and continued afterwards into the follow-up period will be counted only once as concomitant medications/procedures during the 60-week treatment period.
- Concomitant medications/procedures during the follow-up period are medications/procedures taken after the week 60 visit date or date of study day 421 if the week 60 visit date is missing to end of study.

4.4. Rescue Medication and Prohibited Medication During Study

Medications prohibited throughout the entire study are presented in [Table 2](#) and medications prohibited for specific study periods are presented in [Table 3](#).

Table 2: Medications Prohibited Prior to Screening and Throughout the Study

Medication Group	Time Prohibited Before Study (Washout)
Corticosteroids (intra-muscular/ intra-articular/ extended duration implants such as intravitreal etc.)	Prohibited (3 months)
Tricyclic antidepressants/ typical antipsychotics	Prohibited (14 days)
Specific immunotherapy (SIT) with cat allergen or vaccines against cat allergy	Prohibited (6 months)
SIT with any allergen other than cat	Prohibited
Immune directed biologics and/or therapies that would interfere with Type 2 allergic disease or suppress the immune system, including but not limited to anti-IgE, anti IL-5, anti IL-4	Prohibited (6 months)
Methylxanthines	Prohibited (3 days)
Systemic calcineurin inhibitors	Prohibited (14 days)

Table 3: Medications Prohibited During Specific Periods of the Study

Medication Group	Medication Subgroup	Baseline Assessment Period up to Week 12 and Weeks 48 to 60 (Washout)*
Antihistamines	1 st gen, 2 nd gen oral antihistamines/ intranasal antihistamines/ ocular antihistamines	Prohibited except study provided anti-allergy rescue medications (desloratadine, olopatadine)
	Longer acting antihistamines (e.g., Hydroxyzine/ Cyproheptadine)	Prohibited (10 days)
Decongestants	Topical/ oral	Prohibited (3 days)
Leukotriene modifiers		Prohibited (30 days)
Anti cholinergics	Intranasal anticholinergics	Prohibited (12 h)
Corticosteroids	Intranasal	Prohibited except study provided anti-allergy rescue medications (mometasone nasal spray)
	Ocular	Prohibited (14 days)
	Oral/ IV	Prohibited (30 days)
Cromoglycates	Ocular/ intranasal	Prohibited (14 days)

* NOTE: Patients will be provided the study rescue medications (desloratadine, olopatadine, mometasone furoate, or in-class equivalent) starting at their baseline assessment visit during screening. Once the patients start their baseline assessment, they should continue to use the study provided rescue medications and avoid any prohibited medications until the completion of the initial efficacy assessment period (weeks 0 to 12). Similarly, the patients should continue to use the study provided rescue medications and avoid any prohibited medications during the final efficacy assessment period (48 to 60 weeks). Prohibited medications (with specific washout durations) are specified in this table for these time periods. Anti-allergic medications (such as antihistamines, anti-allergic eye drops, anti-allergic nasal sprays) outside of study-related anti-allergic medications are prohibited during baseline and efficacy assessment periods (baseline to week 12 and weeks 48 to 60).

Skin prick testing: Antihistamines should be withheld for 5 days prior to SPT (longer acting antihistamines such as hydroxyzine, cyproheptadine should be withheld for 10 days).

Prohibited medications as specified above have been further categorized into groups based on their expected impact on the efficacy variables. Appropriate data handling methods for analysis for each category are described in Section 5.6. Categories of prohibited medications based on their expected impact on efficacy assessment are defined in Section 10.5.

Medications that fall into each of the categories as specified in Section 10.5 are specified in Table 7 (for CSMS, TNSS, TOSS, DMS and RQLQ(S)+12), Table 8 (for asthma-related endpoints), and Table 9 (for SPT endpoints). For medications that fall into Category 2, blinded adjudication by the study medical director will be implemented before the database lock to determine the potential impact of the use of the prohibited medication on the efficacy assessments. The adjudication procedure will be documented.

4.5. Efficacy Variable

4.5.1. Primary Efficacy Variable

The primary efficacy endpoint in the study is the daily CSMS defined in Section 4.5.5, averaged over the last 12 weeks of the treatment period (weeks 48 to 60).

4.5.2. Key Secondary Efficacy Variables

The key secondary endpoints, specified without order, are:

- Daily TNSS, averaged over the last 12 weeks of treatment period (weeks 48 to 60)
- Percent change from pre-treatment baseline in average CSMS, over the last 12 weeks of the treatment period (weeks 48 to 60)
- Percent change from pre-treatment baseline in average TNSS, over the last 12 weeks of the treatment period (weeks 48 to 60)
- Daily TSS, averaged over the last 12 weeks of the treatment period (weeks 48 to 60)
- Percent change from pre-treatment baseline in average TSS, over the last 12 weeks of the treatment period (weeks 48 to 60)
- Percent change from baseline to the end of treatment (week 60) in cat SPT mean wheal diameter

4.5.3. Other Secondary Efficacy Variables

Other secondary endpoints, specified without order, are:

- Daily CSMS, averaged over the initial 12 weeks of the treatment period (weeks 0 to 12)
- Daily TNSS, averaged over the initial 12 weeks of treatment period (weeks 0 to 12)
- Percent change from pre-treatment baseline in average CSMS, over the initial 12 weeks of the treatment period (weeks 0 to 12)
- Percent change from pre-treatment baseline in average TNSS, over the initial 12 weeks of the treatment period (weeks 0 to 12)
- Percent change from pre-treatment baseline in average TSS, over the initial 12 weeks of the treatment period (weeks 0 to 12)
- Daily TSS score, averaged over the initial 12 weeks of the treatment period (weeks 0 to 12)
- Percent change from pre-treatment baseline in average TOSS, over the initial 12 weeks of the treatment period (weeks 0 to 12)
- Daily TOSS, averaged over the last 12 weeks of the treatment period (weeks 48 to 60)
- Percent change from pre-treatment baseline in average TOSS, over the last 12 weeks of the treatment period (weeks 48 to 60)
- Percent change from baseline to week 12 in FEV1 in patients with asthma
- Percent change from baseline to week 60 in FEV1 in patients with asthma
- Percent change from baseline to week 12 in cat skin prick test (SPT) mean wheal diameter
- Change from baseline to week 12 in FEV1 in patients with asthma
- Change from baseline to week 60 in FEV1 in patients with asthma
- Change from baseline to week 60 in RQLQ(S)+12
- DMS, averaged over the initial 12 weeks of the treatment period (weeks 0 to 12)
- DMS, averaged over the last 12 weeks of the treatment period (weeks 48 to 60)
- Percent change from pre-treatment baseline in average DMS, averaged over the last 12 weeks of the treatment period (weeks 48 to 60)
- Percent change from baseline to end of study (week 72) in cat SPT mean wheal diameter
- Asthma daily symptom score (ADSS), averaged over the initial 12 weeks of the treatment period (weeks 0 to 12), using Asthma Daytime Symptom Diary (ADSD) and the Asthma Nighttime Symptom Diary (ANSO), in patients with asthma

- Asthma daily symptom score (ADSS), averaged over the last 12 weeks of the treatment period (weeks 48 to 60), using Asthma Daytime Symptom Diary (ADSD) and the Asthma Nighttime Symptom Diary (ANS), in patients with asthma
- Daily TOSS, averaged over the initial 12 weeks of the treatment period (weeks 0 to 12)
- Change from baseline to week 60 in ACQ-5 in patients with asthma
- Daily number of nighttime awakenings, averaged over the initial 12 weeks of the treatment period (weeks 0 to 12), in patients with asthma
- Daily number of nighttime awakenings, averaged over the last 12 weeks of the treatment period (weeks 48 to 60), in patients with asthma

4.5.4. Exploratory Variables

The exploratory endpoints are:

- The number of “well days” over the initial 12 weeks (weeks 0 to 12) of the treatment period; “well days” are defined as days when rescue medication is not utilized and the TSS is $\leq 2/18$
- The number of “well days” over the last 12 weeks of the treatment period (weeks 48 to 60); “well days” are defined as days when rescue medication is not utilized and the TSS is $\leq 2/18$
- Percent change from pre-treatment baseline in average ADSS, over the initial 12 weeks of the treatment period (weeks 0 to 12), using ADSD and the ANSD
- Percent change from pre-treatment baseline in average frequency of asthma rescue medication use, defined as the number of puffs of a short-acting bronchodilator and an inhaled steroid over the past 24 hours, over the initial 12 weeks of the treatment period (weeks 0 to 12), in patients with asthma
- Percent change from pre-treatment baseline in average frequency of nighttime awakenings, over the initial 12 weeks of the treatment period (weeks 0 to 12), in patients with asthma
- Percent change from pre-treatment baseline in average DMS, over the initial 12 weeks of the treatment period (weeks 0 to 12)
- Change from baseline to week 12 in RQLQ(S)+12
- Change from baseline to week 12 in Asthma Control Questionnaire 5 Question Version (ACQ-5) in patients with asthma
- Daily frequency of asthma rescue medication use, averaged over the initial 12 weeks of the treatment period (weeks 0 to 12), in patients with asthma
- Daily frequency of asthma rescue medication use, averaged over the last 12 weeks of the treatment period (weeks 48 to 60), in patients with asthma

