# 2.2. Secondary Objectives

The secondary objectives are:

- To assess the reduction of allergic symptoms and use of allergy rescue medications after treatment with REGN1908-1909 versus placebo, as measured by the individual components of the CSMS
- To assess health-related quality of life (HRQoL) as measured by the Rhinoconjunctivitis Quality of Life Questionnaire (RQLQ[S])
- To determine the efficacy of REGN1908-1909, as compared to placebo, to inhibit a wheal-and-flare response to a skin prick test with cat allergen
- To assess the durability of effect in allergic rhinitis and conjunctivitis symptom and medication scores after multiple doses of REGN1908-1909 compared to placebo given every 12 weeks (Q12W)
- To determine the efficacy following multiple doses of REGN1908 1909 compared to placebo at inhibiting a wheal-and-flare response to a skin prick test with cat allergen
- To estimate the effect of REGN1908-1909 on lung function, as compared to placebo, in patients with asthma
- To determine the efficacy of REGN1908-1909 as compared to placebo to reduce asthma symptoms in patients with asthma
- To assess whether there is a difference in asthma rescue medication use in patients with asthma who are treated with REGN1908-1909 compared to placebo
- To assess whether there is a difference in nighttime awakenings in patients with asthma treated with REGN1908-1909 compared to placebo
- To evaluate the short-term and long-term safety and tolerability of REGN1908-1909, including the incidence of hypersensitivity reactions, local injection site reactions, and asthma exacerbations
- To determine systemic exposure of total (free and antigen-bound) antibodies as measured by concentration of REGN1908 and REGN1909
- To assess the immunogenicity of REGN1908 and REGN1909

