# 4.3. Exploratory Endpoints

The exploratory endpoints are:

- The number of "well days" in those who received REGN1908-1909 versus placebo, over the initial 12 weeks (weeks 0 to 12) of the treatment period; "well days" are defined as days when rescue medication is not utilized and the TSS is <2/18
- The number of "well days" in those who received REGN1908-1909 versus placebo, over the last 12 weeks of the treatment period (weeks 48 to 60); "well days" are defined as days when rescue medication is not utilized and the TSS is <2/18
- Percent change from pre-treatment baseline in average ADS score, over the initial 12 weeks of the treatment period (weeks 0 to 12), using ADSD and the ANSD in patients with asthma who receive REGN1908-1909 versus placebo
- Percent change from pre-treatment baseline in average frequency of asthma rescue medication use, over the initial 12 weeks of the treatment period (weeks 0 to 12), in patients with asthma who receive REGN1908-1909 versus placebo
- Percent change from pre-treatment baseline in average frequency of nighttime awakenings, over the initial 12 weeks of the treatment period (weeks 0 to 12), in patients with asthma who receive REGN1908-1909 versus placebo
- Percent change from pre-treatment baseline in average DMS, over the initial 12 weeks of the treatment period (weeks 0 to 12), in patients who receive REGN1908-1909 versus placebo
- Change from baseline to week 12 in RQLQ(S)+12 in patients who receive REGN1908-1909 versus placebo

- Change from baseline to week 12 in Asthma Control Questionnaire 5 Question Version (ACQ-5) in patients with asthma who receive REGN1908-1909 versus placebo
- Daily frequency of asthma rescue medication use, averaged over the initial 12 weeks of the treatment period (weeks 0 to 12), in patients with asthma who receive REGN1908-1909 versus placebo
- Daily frequency of asthma rescue medication use, averaged over the last 12 weeks of the treatment period (weeks 48 to 60), in patients with asthma who receive REGN1908-1909 versus placebo

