#### 9.2.3.5. Rescue Medication Use

Only for patients with asthma, patients will report the number of rescue medication puffs (example-short-acting bronchodilator) by completing the e-diary every evening.

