10.5. Prohibited Medications Relevant for Analysis

Prohibited medications as defined in Section 4.4 have been further categorized into groups based on their expected impact on the efficacy variables and planned data handling method:

- **Category 1** – Medications that are not expected to impact efficacy variables (treatment policy)
- **Category 2** – Medications that require blinded adjudication (considering factors such as the type of medication, indication, timing, and frequency) to determine if data should be handled by treatment policy, composite strategy (in the case of medications that are expected to impact efficacy variables and may be indicative of treatment failure), or hypothetical strategy (in the case of medications that are expected to impact efficacy variables but are not indicative of treatment failure)
- **Category 3** – Medications that are expected to impact efficacy variables, but are not indicative of treatment failure (hypothetical strategy)

These categories have been defined separately for the following groups of endpoints:

- CSMS, TNSS, TOSS, DMS and RQLQ(S)+12 endpoints ([Table 7](#))
- Asthma-related endpoints ([Table 8](#))
- SPT endpoints ([Table 9](#))

Table 7: Prohibited medication categories for CSMS, TNSS, TOSS, DMS and RQLQ(S)+12 endpoints

Category 1	Category 2
Treatment policy	Adjudication to determine treatment policy, composite strategy, or hypothetical strategy
1st gen, 2nd gen oral antihistamines/ intranasal antihistamines/ ocular antihistamines	Corticosteroids (intra-muscular/ intra-articular/ extended duration implants such as intravitreal etc)
Longer acting antihistamines (eg, Hydroxyzine/ Cyproheptadine)	Oral/ IV corticosteroids
Topical/ oral decongestants	Systemic calcineurin inhibitors
Intranasal anticholinergics	
SIT with any allergen other than cat
 
Immune directed biologics and/or therapies that would interfere with Type 2 allergic disease or suppress the immune system, including but not limited to anti-IgE, anti IL-5, anti IL-4
 
Specific immunotherapy (SIT) with cat allergen or vaccines against cat allergy

Intranasal corticosteroids	
Ocular corticosteroids	
Ocular/intranasal cromoglycates	
Methylxanthines	
Leukotriene modifiers	

Table 8: Prohibited medication categories for asthma-related endpoints

Category 1 Treatment policy	Category 2 Adjudication to determine Treatment Policy, Composite Strategy, or Hypothetical Strategy	Category 3 Hypothetical Strategy (Multiple Imputation)

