1st gen, 2nd gen oral antihistamines/ intranasal antihistamines/ ocular antihistamines	Corticosteroids (intra-muscular/ intra-articular/ extended duration implants such as intravitreal etc)	Inhalational Corticosteroids, SABA/LABA/LAMA if not washed out within timeframes specified in the study protocol
Longer acting antihistamines (eg, Hydroxyzine/ Cyproheptadine)	Oral/ IV corticosteroids	
Topical/ oral decongestants	Immune directed biologics and/or therapies that would interfere with Type 2 allergic disease or suppress the immune system, including but not limited to anti-IgE, anti IL-5, anti IL-4	
Intranasal anticholinergics	Specific immunotherapy (SIT) with cat allergen or vaccines against cat allergy	
Intranasal corticosteroids		
Ocular corticosteroids		
Ocular/intranasal cromoglycates		
Methylxanthines		
Leukotriene modifiers		

Table 9: Prohibited medication categories for SPT endpoints

Category 1 Treatment policy	Category 2 Adjudication to determine Treatment Policy, Composite Strategy or Hypothetical Strategy	Category 3 Hypothetical Strategy (Multiple Imputation)
1st gen, 2nd gen intranasal antihistamines/ ocular antihistamines	Immune directed biologics and/or therapies that would interfere with Type 2 allergic disease or suppress the immune system, including but not limited to anti-IgE, anti IL-5, anti IL-4	1st gen, 2nd gen oral antihistamines (5 day window)
Topical/ oral decongestants	Specific immunotherapy (SIT) with cat allergen or vaccines against cat allergy	Longer acting antihistamines (eg, Hydroxyzine/ Cyproheptadine) (10 day window)
Intranasal anticholinergics		
Intranasal corticosteroids		
Ocular corticosteroids		
Ocular/intranasal cromoglycates		
Methylxanthines		
Leukotriene modifiers		
Corticosteroids (intra-muscular/ intra- articular/ extended duration implants such as intravitreal etc)		
Oral/ IV corticosteroids		
Systemic calcineurin inhibitors		
SIT with any allergen other than cat		

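### The SAP's definition of asthma rescue use adds inhaled-steroid puffs that the protocol does not name, so read literally it pulls one exploratory percent-change endpoint towards zero by an unknown amount.

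*SAP*

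**What the plan says.** Protocol 2.2 sets a secondary objective: "To assess whether there is a difference in asthma rescue medication use in patients with asthma". The endpoints that address it are all exploratory (Protocol 4.3, SAP 4.5.4). There are three: the percent change over weeks 0 to 12, and the daily frequency over weeks 0 to 12 and over weeks 48 to 60.

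Protocol 9.2.3.5 describes the data source: "patients will report the number of rescue medication puffs (example-short-acting bronchodilator) by completing the e-diary every evening". The protocol's endpoint wording, "Percent change from pre-treatment baseline in average frequency of asthma rescue medication use, over the initial 12 weeks of the treatment period", names no drug class.

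SAP 4.5.4 inserts a definition into that percent-change endpoint: "defined as the number of puffs of a short-acting bronchodilator and an inhaled steroid over the past 24 hours". It does not repeat the definition for the other two, for example "Daily frequency of asthma rescue medication use, averaged over the last 12 weeks of the treatment period (weeks 48 to 60), in patients with asthma".

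Elsewhere, SAP Table 8 (Section 10.5) puts this entry in Category 3 for asthma-related endpoints: "Inhalational Corticosteroids, SABA/LABA/LAMA if not washed out within timeframes specified in the study protocol". Category 3 is described as "Medications that are expected to impact efficacy variables, but are not indicative of treatment failure (hypothetical strategy".

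**The concern.** The SAP counts a drug class that the protocol does not name as rescue, has no as-needed qualifier, and does not declare the change among its modifications from the protocol (SAP 1.2.4). An inhaled steroid can be regular background treatment. Inhaled corticosteroids are absent from Protocol Tables 1 and 2, and SAP 5.6.2 expects some patients to be on asthma medication at baseline. Nothing in the SAP wording keeps regular puffs out of the count.

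A near-constant background added to both baseline and follow-up enlarges the denominator of a percent change but not its numerator. The result would then depend partly on how many background puffs a patient takes and not only on the need for a reliever. Because one of the three endpoints carries a definition and two do not, the same quantity could also be computed in two ways.

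**Working it through.** The documents give no figure for asthma rescue use, so there is none to reproduce.

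**Inputs.** From the documents: the two definitions above, and at least 30% of patients expected to have asthma (Protocol 1), which is 0.30 × 630 = 189, or about 94 per arm. Assumed, because the documents are silent: baseline reliever use s of 0.5 to 4 puffs/day, constant steroid use c of 1 to 4 puffs/day, and a true reliever reduction r of 30%.

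**Percent change.**
- Reliever puffs only: [(1−r)s − s]/s = −r, which is −30%.
- Combined count: [((1−r)s + c) − (s + c)]/(s + c) = −r·s/(s+c).

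| s | c = 1 | c = 2 | c = 4 |
|---|---|---|---|
| 0.5 | −10% | −6% | −3.3% |
| 1 | −15% | −10% | −6% |
| 2 | −20% | −15% | −10% |
| 4 | −24% | −20% | −15% |

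The extremes are 30 × 0.5/4.5 = 3.3 and 30 × 4/5 = 24.

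**Absolute change.** [(1−r)s + c] − (s + c) = −r·s, so c cancels. At s = 1 the change is −0.30 puffs/day under either count.

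**Effect on a comparison (illustrative simulation).** The set-up was 1,000 trials per setting, 94 patients per arm, a mean of about 1 reliever puff/day, a 30% reduction on active, 25% to 100% of patients on a constant 2 or 4 steroid puffs/day, and unadjusted t-tests.
- Percent change: the between-arm difference falls from about −30 points to between −25 and −6. Power falls from about 96% to between 84% and 93%. The loss is modest because constant puffs shrink the spread as well.
- Daily frequency: the mean difference stays at about −0.3 puffs/day. Unadjusted power falls from about 57% to between 16% and 35% when a quarter or half of patients use the steroid, and does not fall when all do. A change-from-baseline comparison keeps about 82%, so an ANCOVA with baseline as covariate would recover much of the loss.

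The distributions in the simulation are also assumed. It shows the pattern, not this trial's size of effect.

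**The case against.** A reader might infer that maintenance controller puffs overwhelm the reliever signal. The documents do not support that. The SAP defines rescue use and never says that maintenance puffs are counted. The only data source described is a diary item for rescue puffs, with other treatments recorded as concomitant medication. The phrase could mean a steroid taken as rescue, or a combined inhaler. The protocol's bronchodilator is an example and not a closed list. Protocol 8.9.2, read literally, allows unlisted medications only outside the baseline and efficacy periods. These points stand, and they make the dilution conditional. They do not remove the fault, because the written rule has no as-needed qualifier.

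A reader might also infer that the measure can change sign. Suppose a patient halves reliever use from 2 to 1 puff while steroid use rises from 2 to 4: the score is (5 − 4)/4 = +25%, against a true −50%. The arithmetic is right, but this is one invented patient with two simultaneous changes. Nothing in the documents says how common this is or that it would favour an arm.

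The conflict with Table 8 has limits too. The same entry lists short-acting bronchodilators and refers to washout times, so it may have been written with spirometry in mind. However, the table covers asthma-related endpoints in general, and the SAP does not say whether rescue counts fall outside it. The washout examples in Protocol 9.2.2.10 do not include inhaled steroids.

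Finally, a count limited to short-acting bronchodilators could drop steroid puffs truly taken as rescue. That is correct, and the fix below is worded to avoid it.

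**Conclusion.** The mismatch is real, undeclared and minor. Read literally, the SAP rule attenuates the weeks 0 to 12 percent change by s/(s+c). The size is unknown. Under the assumed ranges a true 30% reduction reads as about 3% to 24%, provided that maintenance steroid puffs do enter the count and stay constant. On the same condition, the absolute between-arm difference in puffs is unaffected.

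The definition is written into one endpoint, and whether it governs the two daily-frequency endpoints is not stated. All three are exploratory and outside the testing hierarchy in SAP 5.6.3, so no confirmatory test, alpha allocation or sample size changes. The point still merits correction because these are the only endpoints serving the secondary objective on asthma rescue use.

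**What to change.** Amend the SAP before database lock:

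- Reconcile SAP 4.5.4 with Protocol 9.2.3.5. Count only puffs recorded as rescue in the diary, name the diary items used, and exclude maintenance inhaled-steroid puffs.
- If maintenance puffs are collected, summarise them separately by arm.
- Apply that one definition to all three asthma rescue endpoints and list the change in SAP 1.2.4.
- State whether Table 8, Category 3 applies to the rescue counts, and make the two consistent.
- Check the zero-baseline rule in SAP 6.2. It assigns +100% whenever baseline is 0 and the later value is positive, however small. Without steroid puffs, more patients may have a zero baseline.

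This costs SAP wording only if the diary already separates rescue from maintenance puffs. If it does not, one diary field is needed, and that would help only entries made after the change.
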